Official Title: Oxalobacter Formigenes Colonization and Oxalate Excretion in Healthy Adults

NCT#: 03752684

Document Date: May 22, 2025

STUDY PROTOCOL

Objective of the study

The primary objective of the study was to determine if healthy adults can be colonized with Oxalobacter formigenes, a naturally occurring oxalate degrading intestinal bacterium, and if colonization results in a decrease in urinary oxalate excretion on a fixed diet.

Study Design

This study was designed as a sequential, diet-controlled study. The study recruited healthy adults from the Greater Birmingham area. The individuals were recruited, consented, and had blood samples collected at the UAB CCTS Clinical Research Unit. Sample processing, data acquisition and analysis was performed in the Urology Stone Research Laboratory.

- Inclusion criteria: not colonized with Oxalobacter formigenes, mentally competent adults without history of kidney stones, who are able to read and comprehend the consent form (written in English); >18 and <65 yrs; BMI 18.5-40 kg/m2; good health as judged from a medical history without other medical comorbidities. individuals will need a normal blood comprehensive metabolic panel.
- Exclusion criteria: colonized with Oxalobacter formigenes, history of any hepatic, renal (including kidney stone disease), bowel or endocrine disease (including diabetes) or any other condition that may influence the absorption, transport or urine excretion of ions, which will compromise the interpretation of results; abnormal blood metabolic profiles; poor 24 hour urine collections judged by 24 hour urine creatinine excretion (indicative of not collecting all urine in 24 hour period); pregnancy, intention to become pregnant in the near future, or lactation; <18 and > 65 years of age; BMI<18.5 >40 kg/m2

Study Methods

Screening. The screening phase involved a fasted blood draw for comprehensive metabolic profile (CMP), two 24hr urine collections (creatinine) and stool collections on self-choice diets. Screening blood tests were used as a health assessment, and urinary creatinine as measure of the candidates' ability to accurately collect urine. Stool at screening was used to test for *O. formigenes* colonization. If negative, participants were further tested after consuming a high oxalate containing meal.

Pre-Colonization Fixed Diet Study: Participants who passed screening collected stool and 24-hour urine specimens while ingesting a moderately high oxalate (210 – 240 mg/day) and low calcium (500 - 700 mg calcium/day) diet. For reference, a healthy diet rich in whole grain products, fruits and vegetables may contain close to 200 mg of oxalate per day, and the recommended dietary calcium intake per day for calcium oxalate kidney stone formers is 1000 mg. Twenty-four-hour urine and stool specimens were collected on days 3-5 of each dietary phase to allow for dietary equilibration. Lack of colonization with *O. formigenes* (pre-colonization phase) was again confirmed by stool culture.

Oxalobacter formigenes colonization procedure: Following completion of the pre-colonization controlled diet, participants ingested live *O.formigenes*, cells spread on a sandwich. One week later participants collected stool for colonization culture testing.

Post-Colonization Fixed Diet Study: Successfully colonized participants repeated stool and urine collections on the same controlled diet.

Assays: Urine and stool oxalate was measured in urines and stool by ion chromatography coupled with mass spectrometry.

Statistical Analysis Plan

The primary outcome measure was decrease in urinary oxalate content after colonization with O. formigenes on the fixed diet. The secondary outcome was decrease in stool oxalate content after colonization with O. formigenes on the fixed diet.

The means of oxalate content of repeated urine and stool collections for each phase (pre and post colonization) were used, and the decrease in oxalate content after colonization determined for each participant. Paired comparisons were performed using linear mixed-effects models (for repeated measures). The covariates included gender, body mass index, age, and a dichotomous variable denoting loss of colonization during the follow-up period (adjusted analyses); these covariates were included because of potential associations with endogenous oxalate synthesis or gut permeability and absorption. Statistical tests were two-sided and were performed using a significance level of 5%. Statistical analyses were performed using SAS software (version 9.4; SAS Institute, Cary, NC). PROC MIXED of SAS was used to perform linear mixed effects models analyses. The sample size was selected based on feasibility considerations for this pilot Basic Experimental Study in Humans (BESH).

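### The loss-of-colonization covariate, read as a main effect, cancels from the paired pre/post contrast, so the adjusted decrease does not account for loss

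*Combined protocol and SAP*

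**What the plan says.** **Statistical Analysis Plan.** Repeated urine and stool collections are averaged within each phase, and "the decrease in oxalate content after colonization determined for each participant". "Paired comparisons were performed using linear mixed-effects models (for repeated measures"), fitted in PROC MIXED. For the adjusted analyses, "The covariates included gender, body mass index, age, and a dichotomous variable" for loss, in full "a dichotomous variable denoting loss of colonization during the follow-up period (adjusted analyses"). One reason is given for all four: possible links with the body's own oxalate synthesis or with gut permeability and absorption. The fixed-effect terms, the coding of the flag and the covariance structure are not given, and no covariate-by-phase term is mentioned.

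**Study Methods.** After ingestion of the organism, "One week later participants collected stool for colonization culture testing". Then "Successfully colonized participants repeated stool and urine collections on the same controlled diet". On timing within a phase, "Twenty-four-hour urine and stool specimens were collected on days 3-5 of each dietary phase to allow for dietary equilibration".

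**Not stated.** The documents do not define the follow-up period, how or when loss was determined, how many participants lost colonization, or the sample size (chosen on feasibility). Stool was collected in the post phase, but the only post-ingestion culture described for colonization is the one at one week, before that phase.

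**The concern.** Gender, BMI and age are traits that a participant brings to the study. Loss of colonization can occur only after ingestion, so it is a post-exposure event, and the reason given for the covariates does not fit it. The flag is also the plan's only provision for loss of the exposure.

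The objective asks "if colonization results in a decrease in urinary oxalate excretion on a fixed diet". A reader of the adjusted result would take it as a decrease with loss, gender, BMI and age allowed for. If the covariates drop out of the contrast, the adjusted figure merely repeats the unadjusted one. Should some participants have lost the organism by the time of the collections, both figures average over colonized and no-longer-colonized people.

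**Working it through.** The plan states no sample size, effect or variance, so there is no figure of its own to reproduce.

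**1. Algebra on the natural reading.** For participant *i* and phase *j* (0 = pre, 1 = post), let

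y_ij = μ + δ·phase_j + x_i′β + u_i + e_ij,

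where x_i holds gender, BMI, age and the loss flag, each constant within a participant. Then

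d_i = y_i,post − y_i,pre = δ + (e_i,post − e_i,pre).

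The term x_i′β has gone. With complete pairs, the estimate of δ is the mean of d_i with or without the covariates.

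**2. Numerical check.** Inputs are assumed: change −8 if colonization is kept and 0 if lost, between-person SD 8, within-person SD 4. REML mixed models were fitted to nine generated data sets (N = 12, 20, 40; nominal loss 20%, 30%, 50%). Adjusted, unadjusted and raw mean paired differences agreed to four decimals, and standard errors to within 0.0001, under both random-intercept and unstructured covariance. Two examples at 30% loss:

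| N | Unadjusted (SE) | Adjusted, main effects (SE) | Retained group, phase-by-status (SE) | Lost group |
|---|---|---|---|---|
| 20 | −5.37 (1.95) | −5.37 (1.95) | −9.26 (1.71) | +3.70 |
| 40 | −5.32 (1.23) | −5.32 (1.23) | −8.73 (1.10) | +2.64 |

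The adjusted figure is the weighted average of the two groups: for N = 20, 0.7 × (−9.26) + 0.3 × 3.70 = −5.37.

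**3. Other codings.** In 300 generated data sets with N = 20, 4 lost before the collections, and the decrease while colonized set to 1, the mean estimates (Monte Carlo SE about 0.01) were:

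- flag as main effect: 0.798
- phase-by-status term, retained group: 0.986
- individual decrease regressed on the flag, retained as reference: 0.989
- flag set only in the post phase: 0.988

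The last three estimate a different quantity from the first: the decrease in those who kept colonization.

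**4. Incomplete pairs.** With 3 of 20 post means missing at random and 4 lost (300 data sets), adjusted and unadjusted decreases differed by at most 0.046 of the decrease. Both averaged 0.80, so the flag still did not recover the decrease while colonized.

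**5. What loss could do to the average.** Assume a fraction p lose colonization, loss removes the effect, and days 3-5 give three equally weighted collections, of which a share f is affected. The average decrease, relative to the decrease while colonized, is 1 − p·f:

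| Loss occurs | f | p = 10% | p = 20% | p = 30% |
|---|---|---|---|---|
| before the day 3 collection | 1 | 0.90 | 0.80 | 0.70 |
| after day 3 | 2/3 | 0.93 | 0.87 | 0.80 |
| after day 4 | 1/3 | 0.97 | 0.93 | 0.90 |
| after day 5 | 0 | 1.00 | 1.00 | 1.00 |

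**6. Precision of a retained-group estimate.** If the variance of the paired differences is the same in all participants as in the retained group, the retained-group SE is larger by 1/√(1−p): 1.05, 1.12, 1.20. If loss removes the effect, mixing the groups adds p(1−p) times the squared decrease to the overall variance. Take a within-person SD of half the decrease, so that the difference variance is 2 × 0.5² = 0.5 of the squared decrease. Then:

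- retained/all = √{0.5 / [(1−p)(0.5 + p(1−p))]} = 0.97, 0.97, 1.00
- lost/all = √{0.5 / [p(0.5 + p(1−p))]} = 2.9, 1.9, 1.5

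for p = 10%, 20%, 30%.

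**The case against.** The plan does not write out its model. It says that a decrease was determined for each participant, and regressing that decrease on the covariates is a fair reading under which the flag does not cancel. This stands: strictly, the documents show an underspecified model, and the cancellation belongs to the natural reading. It does not rescue the plan, because the other codings change what is estimated and condition on a post-exposure event without saying so.

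Complete pairs are also an assumption. Participants who were not colonized have pre-phase data only, and the plan does not say whether they stay in the model. If they do, cancellation is approximate, with the small differences shown above.

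A reader might infer that the flag biases the primary result. It does not: on the natural reading it leaves the estimate alone, and cancellation of participant-level main effects is a general property of paired models. A reader might also infer that the trial's decrease is understated by 10% to 30%. The documents do not support that either. The dilution table describes the unadjusted mean and would be the same with no flag in the plan. Entry to the post phase required successful colonization, and nothing places any loss before the collections.

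Finally, this is a short, past-tense account of a feasibility-sized pilot, so conduct cannot change. The analysis description and the reporting still can.

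**Conclusion.** The concern holds in a limited form and should be fixed. As main effects with complete pairs, all four covariates leave the pre/post decrease exactly where it was, whatever the effect size, N or loss rate. The adjusted result then cannot be described as accounting for loss, gender, BMI or age. Under another coding, it answers an undeclared question about those who kept colonization.

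The unadjusted paired decrease remains a valid average over participants who entered the post phase. Whether it differs from the decrease while colonized depends on the rate and timing of loss, which the documents do not give. On the illustrative assumptions, the ratio runs from 0.70 to 1.00. Confidence is medium because the model is not written out.

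**What to change.** 1. Keep the unadjusted paired decrease in all participants who entered the post phase as the main result. Do not present main-effect adjustment as accounting for loss, gender, BMI or age.
2. Write out the model, define the follow-up period, and say how and when loss was determined.
3. Replace the loss main effect with a supportive phase-by-status term. Status should be colonization at the post-phase collections, taken from data already recorded; loss after the last collection does not count. Give the decrease with 95% CI in the retained group, and only describe the lost group if it is small.
4. Label that analysis post hoc and non-randomized, because status is itself post-exposure.
5. If loss cannot be dated relative to the collections, report the main result only and say so.

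The cost is revised wording and one supportive model, with no new data. Precision in the retained group need not fall much: by the ratios above it is between about unchanged and 20% worse at up to 30% lost. The lost group will be imprecise. With an assumed N of 20, the chance of having 0 or 1 lost participants is 39%, 7% and 1% at 10%, 20% and 30% loss; with N of 10 it is 74%, 38% and 15%.
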